### **General PK Parameter Rules**

- Actual sampling times will be used in the final analyses of individual PK parameters, except for non-bolus pre-dose sampling times which will be set to zero.
- $C_{\max}$  and  $t_{\max}$  will be reported from observed values. If  $C_{\max}$  occurs at more than one time point,  $t_{\max}$  will be assigned to the first occurrence of  $C_{\max}$ .
- AUC parameters will be calculated using a combination of the linear and logarithmic trapezoidal methods (linear-log trapezoidal rule). The linear trapezoidal method will be applied up to  $t_{\max}$  and then the logarithmic trapezoidal method will be used after  $t_{\max}$ . The minimum requirement for the calculation of AUC will be the inclusion of at least three consecutive concentrations above the lower limit of quantification, with at least one of these concentrations following  $C_{\max}$ .
- AUC( $0-\infty$ ) values where the percentage of the total area extrapolated is more than 20% will be flagged. Any AUC( $0-\infty$ ) value excluded from summary statistics will be noted in the footnote of the summary table.
- Half-life ( $t_{1/2}$ ) will be calculated, when appropriate, based on the apparent terminal log-linear portion of the concentration-time curve. The start of the terminal elimination phase for each participant will be defined by visual inspection and generally will be the first point at which there is no systematic deviation from the log-linear decline in plasma concentrations. Half-life will only be calculated when a reliable estimate for this parameter can be obtained comprising of at least 3 data points. If  $t_{1/2}$  is estimated over a time window of less than 2 half-lives, the values will be flagged in the data listings. Any  $t_{1/2}$  value excluded from summary statistics will be documented in the footnote of the summary table.
- A uniform weighting scheme will be used in the regression analysis of the terminal log-linear portion of the concentration-time curve.
- The parameters based on observed last quantifiable drug concentration will be reported.

### **Individual PK Parameter Rules**

- Only quantifiable concentrations will be used to calculate PK parameters with the exception of special handling of certain concentrations reported below the lower limit of quantitation (BQL). Plasma concentrations reported as BQL will be set to a value of zero when all of the following conditions are met:

- The compound is non-endogenous.
- The samples are from the initial dose period for a participant or from a subsequent dose period following a suitable wash-out period.
- The time points occur before the first quantifiable concentration.
- All other BQL concentrations that do not meet the above criteria will be set to missing.
- Also, where two or more consecutive concentrations are BQL towards the end of a profile, the profile will be deemed to have terminated and therefore any further quantifiable concentrations will be set to missing for the calculation of the PK parameters unless it is considered to be a true characteristic of the profile of the drug.

### **Individual Concentration vs. Time Profiles**

- Individual concentrations will be plotted utilizing actual sampling times.
- The terminal point selections will be indicated on a semi-logarithmic plot.

### **Average Concentration vs. Time Profiles**

- The average concentration profiles will be graphed using scheduled (nominal) sampling times.
- The average concentration profiles will be graphed using arithmetic average concentrations.
- The pre-dose average concentration for single-dose data from non-endogenous compounds will be set to zero. Otherwise, only quantifiable concentrations will be used to calculate average concentrations.
- Concentrations at a sampling time outside sampling time window specified in Section 1.3.1 in the protocol, or  $\pm 10\%$ , will be excluded from the average concentration profiles.
- Concentrations excluded from the mean calculation will be documented in the CSR.
- A concentration average will be plotted for a given sampling time only if 2/3 of the individual data at the time point have quantifiable measurements that are within the sampling time window specified in the protocol or  $\pm 10\%$ . An average concentration estimated with less than 2/3 but more than 3 data points may be displayed on the mean concentration plot if determined to be appropriate and will be documented within the CSR.

## **Treatment of Outliers during Pharmacokinetic Analysis**

Application of this procedure to all PK analyses is not a requirement. Rather, this procedure provides justification for exclusion of data when scientifically appropriate. This procedure describes the methodology for identifying an individual value as an outlier for potential exclusion, but does not require that the value be excluded from analysis. The following methodology will not be used to exclude complete profiles from analysis.

### Data within an Individual Profile

A value within an individual profile may be excluded from analysis if any of the following criteria are met:

- For PK profiles during single dosing of non-endogenous compounds, the concentration in a pre-dose sample is quantifiable.
- For any questionable datum that does not satisfy the above criteria, the profile will be evaluated and results reported with and without the suspected datum.

### Data between Individual Profiles

1. If  $n < 6$ , then the dataset is too small to conduct a reliable range test. Data will be analyzed with and without the atypical value, and both sets of results will be reported.
2. If  $n \geq 6$ , then an objective outlier test will be used to compare the atypical value to other values included in that calculation:
  - a. Transform all values in the calculation to the logarithmic domain.
  - b. Find the most extreme value from the arithmetic mean of the log transformed values and exclude that value from the dataset.
  - c. Calculate the lower and upper bounds of the range defined by the arithmetic mean  $\pm 3 \times SD$  of the remaining log-transformed values.
  - d. If the extreme value is within the range of arithmetic mean  $\pm 3 \times SD$ , then it is not an outlier and will be retained in the dataset.
  - e. If the extreme value is outside the range of arithmetic mean  $\pm 3 \times SD$ , then it is an outlier and will be excluded from analysis.

If the remaining dataset contains another atypical datum suspected to be an outlier and  $n \geq 6$  following the exclusion, then repeat step 2 above. This evaluation may be repeated as many times as necessary, excluding only one suspected outlier in each iteration, until all data remaining in the dataset fall within the range of arithmetic mean  $\pm 3 \times SD$  of the log-transformed values.

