## 7. SAMPLE SIZE JUSTIFICATION

Approximately 60 participants will be enrolled and randomly assigned to study intervention (10 per group/dose level; 7 ramucirumab:3 placebo) to obtain at least 48 evaluable participants overall for an estimated total of at least 8 evaluable participants per intervention group (6 ramucirumab and at least 2 placebo). The sample size is not powered on the basis of statistical hypothesis testing. A participant will be considered evaluable when the participant completes up to 40 days of study procedures. When a participant does not complete up to 40 days of study procedures, the sponsor will be consulted if the participant will need to be replaced.

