### Reporting of Excluded Values

Individual values excluded as outliers will be documented in the CSR. Approval of the CSR will connote approval of the exclusion.

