### 9.3.2 Pharmacokinetic Statistical Methodology

Ramucirumab bioavailability will be estimated. PK parameters will be evaluated to estimate ramucirumab  $AUC_{(0-\infty)}$  and  $C_{max}$  dose proportionality following SC administration in the dose range investigated. Log-transformed ramucirumab  $C_{max}$  and  $AUC_{(0-\infty)}$  parameters will be evaluated in a linear mixed effects model with fixed effects for dose (Groups 1, 4, and 5 who received 350 mg will be combined if appropriate). The treatment differences will be back-transformed to present the ratios of geometric means and the corresponding 90% confidence interval.

For ramucirumab SC dosing PK parameters, the  $t_{max}$  will be analyzed using a Wilcoxon rank-sum test. Estimates of the median difference based on the observed medians, 90% CIs, and p-values from the Wilcoxon test will be calculated to assess similarity or not in  $t_{max}$  between dose level groups 1, 4, 5 combined compared to group 2 and group 6.

The above-mentioned analysis investigating the relationship (e.g. linearity/proportionality) between ramucirumab PK parameters and dose may be adjusted/repeated in the event of significant difference in PK between the 350 mg SC groups (Group 1, 4, 5). Such difference would indicate significant impact of either injection volume or drug product concentration on the PK. In this scenario, the analysis, investigating the relationship (e.g. linearity/proportionality) between ramucirumab PK parameters and dose, may be repeated by excluding the data from one or two of the 350 mg SC group.

Comparison of  $AUC_{(0-\infty)}$ ,  $C_{max}$  and  $t_{max}$  between Group 1 and Group 4 will enable to assess the effect of changing the drug product concentration on the exposure. The log-transformed  $AUC_{(0-\infty)}$ ,  $C_{max}$  and  $t_{max}$  will be the response variable, and the drug product concentration (that is, Group 1 and Group 4) is the explanatory variable.

Comparison of  $AUC_{(0-\infty)}$ ,  $C_{max}$  and  $t_{max}$  between Group 1 and Group 5 will enable to assess the effect of changing the volume injected at one site of injection on the exposure. The log-transformed  $AUC_{(0-\infty)}$ ,  $C_{max}$  and  $t_{max}$  will be the response variable, and the volume injected (that is, Group 1 and Group 5) is the explanatory variable.

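### The SAP's 3-SD outlier test, used routinely, would flag 27–31% of outlier-free groups of 6–7, and no all-data result is required when a flagged value is dropped

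*SAP*

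**What the plan says.** The rule is in SAP 9.3.1, under Data between Individual Profiles. Below n=6 the SAP regards the data as too few for a range test and requires dual reporting: "Data will be analyzed with and without the atypical value, and both sets of results will be reported". From n=6 the values are log-transformed and the one furthest from the mean is removed. Limits of mean ± 3 SD are computed from the remaining values. If the removed value falls outside them, "then it is an outlier and will be excluded from analysis". The step may be repeated while at least six values remain.

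The preamble, Treatment of Outliers during Pharmacokinetic Analysis, is permissive. It says that "this procedure provides justification for exclusion of data when scientifically appropriate" and that the method "does not require that the value be excluded from analysis". It also rules out removing whole profiles this way. Under Reporting of Excluded Values, the only requirement is: "Individual values excluded as outliers will be documented in the CSR".

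SAP section 7 plans 7 ramucirumab participants per group, with a minimum evaluable set of "6 ramucirumab and at least 2 placebo". The PK population contains ramucirumab recipients only, so a single-group PK calculation has 6 or 7 values. For the dose comparison, SAP 9.3.2 will "present the ratios of geometric means and the corresponding 90% confidence interval". Groups 1, 4 and 5 are combined if appropriate. If those groups differ, the dose analysis "may be repeated by excluding the data from one or two of the 350 mg SC group".

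**The concern.** A 3-SD limit sounds strict, but three features make it loose at this size. The SD comes from only five or six values. The value tested is always the most extreme one. The multiplier is the same at every n. Ordinary data will therefore often meet the criterion, and meeting it is what the SAP offers as justification for removal.

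AUC(0-∞) and Cmax are primary PK endpoints. Dropping genuine extremes shrinks the geometric CV and makes the 90% intervals too narrow. The with/without safeguard stops at n=6, which is the planned minimum group size and the point where the test is least reliable. Documenting an exclusion tells the reader that a value was removed, but does not supply the estimate and interval with it included.

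The preamble (exclusion not required) and the final step (value will be excluded) also give different instructions for the same flagged value.

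**Working it through.** The documents give no error rate for the test, so there is no planned figure to reproduce.

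**Inputs.** The multiplier of 3, the leave-one-out mean and SD, and the n≥6 threshold come from SAP 9.3.1. The 6–7 active participants per group come from SAP 7. Pooling Groups 1, 4 and 5 gives 3×6 = 18 to 3×7 = 21. Log-normality is assumed, as SAP 9.1 does for AUCs and Cmax.

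**False-flag rate.** With no outlier, a value's deviation from the mean of the rest, divided by SD(rest) × √(1 + 1/(n−1)), follows a t distribution on n−2 df. The 3-SD rule is therefore a cut-off of c = 3/√(1 + 1/(n−1)) on that t. Because the most extreme of n values is tested, the chance of a flag per group is close to n × p, where p = 2P(t > c). It does not depend on the mean or the CV.

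| n | c | df | p | n × p | Simulated |
|---|---|---|---|---|---|
| 6 | 3/√1.2 = 2.739 | 4 | 0.0520 | 31.2% | 31.2% |
| 7 | 3/√1.1667 = 2.777 | 5 | 0.0390 | 27.3% | 27.3% |
| 18 | 2.916 | 16 | 0.0101 | 18.2% | 18.2% |
| 21 | 2.928 | 19 | 0.0086 | 18.1% | 18.0% |

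The simulation used 1,000,000 groups at n=6 and 7, and 400,000 at n=18 and 21.

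**Across the study.** For one parameter in Groups 1–5, treated as independent, the chance of at least one flag is 1 − (1 − 0.273)⁵ = 80% at n=7 and 1 − (1 − 0.312)⁵ = 85% at n=6. With repetition at n=7, 31% of flagged groups lose a second value, which is 8.5% of all groups.

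**Effect in a flagged group.** Dropping the value lowers the average log-scale SD from 0.95 to 0.51 of the true SD at n=6 (47% lower), and from 0.96 to 0.55 at n=7 (42% lower).

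**Effect on the 90% interval.** The rule was applied to each arm of outlier-free trials, repeated while n≥6, with every flagged value dropped (40,000 trials per design).

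| Design | Coverage, flags dropped | Mean pooled variance / true |
|---|---|---|
| 6 v 6 | 81.1% (second run 81.5%) | 0.794 |
| 7 v 7 | 82.3% (second run 82.5%) | 0.824 |
| 18 v 6 | 85.3% | 0.899 |
| 21 v 7 | 85.8% | 0.908 |

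With all data kept, coverage was 89.6–90.2%. Variance is understated by about 20% (6 v 6), 18% (7 v 7) and 9–10% (pooled designs).

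**If only some flags are acted on.** With the dropped flags chosen at random, two-group coverage is 88.0%, 85.8% and 83.7% at n=6 when 25%, 50% and 75% are dropped. At n=7 it is 88.3%, 86.5% and 84.5%.

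**Reporting.** Below n=6, both sets of results are required. For a questionable point within a profile, both are also required. From n=6, the value is documented in the study report and appears in the listings under SAP 9.1. No section requires the analysis with the value included.

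**The case against.** The strongest reply is that the SAP does not tell anyone to test every group. A value must first look atypical, use of the procedure is optional, and exclusion is a scientific judgement. Many chance flags arise because the other values happen to cluster, so the flagged value is not far away in absolute terms and might never be challenged. Suppose only values at least 2-fold from the geometric mean of the rest were questioned. The flag rate at n=6–7 would then be about 0.7%, 9% or 19% for a CV of 20%, 30% or 40%. With a 1.5-fold screen it would be about 14–15%, 24–26% or 26–29%. This point stands as a limit on the size: 27–31% is the routine-use rate, and actual removals may be far fewer or close to it. The SAP gives neither a CV nor a definition of atypical, so the range cannot be narrowed. For the same reason, the random-dropping coverages are illustrations, not predictions.

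It can also be said that the SAP specifies a 90% interval only for the dose comparison, where pooling puts worst-case coverage at 85–86%. That is correct. For Group 1 v 4 and Group 1 v 5 the interval is inferred. The specified interval returns to 6–7 per arm only if two of the 350 mg groups are left out, which SAP 9.3.2 permits.

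The test might be meant for concentrations in mean profiles instead of PK parameters. The SAP speaks generally of the values in a calculation, and under a heading about data between profiles that naturally includes AUC and Cmax.

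Finally, no hypothesis test or equivalence margin is planned, and a reader could recompute from the listings. The harm is therefore to estimates, CVs and interval widths, not to a confirmatory error rate. But leaving readers to redo the analysis does not replace reporting it.

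**Conclusion.** The concern holds and should be fixed. At the planned 6–7 per group, the criterion is met by 27–31% of outlier-free groups per parameter under routine use, and by about 18% of pooled 350 mg sets. Acting on every flag reduces a nominal 90% interval to about 81–82% coverage for two single groups and 85–86% for the pooled dose comparison. These are worst-case figures. They assume log-normal data, use of the test on PK parameters, and removal of every flagged value; discretion lowers them by an amount the documents do not fix.

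The reporting gap depends on none of those assumptions: from n=6 upward nothing requires the all-data result, although the SAP requires it for smaller sets. The optional and mandatory wordings on exclusion also need to be reconciled.

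**What to change.** Amend SAP 9.3.1 as follows:

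- Make the analysis of all data primary at every n.
- Use the 3-SD test only to flag values for scientific review.
- Extend the with/without reporting that already applies below n=6 to n≥6, showing the geometric mean, geometric CV, ratio and 90% interval both ways.
- Reword the final step so that it agrees with the preamble that exclusion is not automatic.

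A size-specific multiplier is optional and not needed for the fix. For a 5% false-flag rate per group it would be about 5.3 SD at n=6, 4.7 SD at n=7 and 3.6 SD at n=18–21.

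The cost is a few sentences of SAP text and one extra table when a value is flagged. Reported CVs and intervals may be slightly wider.

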### Reporting of Excluded Values

Individual values excluded as outliers will be documented in the CSR. Approval of the CSR will connote approval of the exclusion.

### 9.3.2 Pharmacokinetic Statistical Methodology

Ramucirumab bioavailability will be estimated. PK parameters will be evaluated to estimate ramucirumab  $AUC_{(0-\infty)}$  and  $C_{max}$  dose proportionality following SC administration in the dose range investigated. Log-transformed ramucirumab  $C_{max}$  and  $AUC_{(0-\infty)}$  parameters will be evaluated in a linear mixed effects model with fixed effects for dose (Groups 1, 4, and 5 who received 350 mg will be combined if appropriate). The treatment differences will be back-transformed to present the ratios of geometric means and the corresponding 90% confidence interval.

For ramucirumab SC dosing PK parameters, the  $t_{max}$  will be analyzed using a Wilcoxon rank-sum test. Estimates of the median difference based on the observed medians, 90% CIs, and p-values from the Wilcoxon test will be calculated to assess similarity or not in  $t_{max}$  between dose level groups 1, 4, 5 combined compared to group 2 and group 6.

The above-mentioned analysis investigating the relationship (e.g. linearity/proportionality) between ramucirumab PK parameters and dose may be adjusted/repeated in the event of significant difference in PK between the 350 mg SC groups (Group 1, 4, 5). Such difference would indicate significant impact of either injection volume or drug product concentration on the PK. In this scenario, the analysis, investigating the relationship (e.g. linearity/proportionality) between ramucirumab PK parameters and dose, may be repeated by excluding the data from one or two of the 350 mg SC group.

Comparison of  $AUC_{(0-\infty)}$ ,  $C_{max}$  and  $t_{max}$  between Group 1 and Group 4 will enable to assess the effect of changing the drug product concentration on the exposure. The log-transformed  $AUC_{(0-\infty)}$ ,  $C_{max}$  and  $t_{max}$  will be the response variable, and the drug product concentration (that is, Group 1 and Group 4) is the explanatory variable.

Comparison of  $AUC_{(0-\infty)}$ ,  $C_{max}$  and  $t_{max}$  between Group 1 and Group 5 will enable to assess the effect of changing the volume injected at one site of injection on the exposure. The log-transformed  $AUC_{(0-\infty)}$ ,  $C_{max}$  and  $t_{max}$  will be the response variable, and the volume injected (that is, Group 1 and Group 5) is the explanatory variable.

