9.1. Statistical Hypotheses

Formal statistical hypothesis testing is not planned. Therefore, adjustments for multiple testing do not apply.

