9.4.2. Pharmacokinetic Analyses

9.4.2.1. Pharmacokinetic Parameter Estimation

Pharmacokinetic parameter estimates for ramucirumab will be calculated by standard noncompartmental methods of analysis.

The primary parameters for analysis will be t_{max} , C_{max} , and AUC of ramucirumab following IV and SC administration and bioavailability following SC administration. Other noncompartmental parameters, such as half-life, IV clearance, volume of distribution, apparent clearance, and volume of distribution following IV and SC ramucirumab administration may be reported.

In addition to noncompartmental analysis, non-linear mixed-effect modelling analysis of the Study JVDT PK data will be performed. This model will enable to estimate mean and variability (variance) of ramucirumab PK parameters following SC administration and to investigate potential covariate explaining that variability.

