9.4.2.2. Pharmacokinetic Statistical Inference

Pharmacokinetic parameters will be evaluated to estimate ramucirumab AUC and C_{max} dose proportionality following SC administration in the dose range investigated. Log-transformed ramucirumab C_{max} and AUC parameters will be evaluated in a linear mixed-effects model with fixed effects for dose (Groups 1, 4, and 5 who received 350 mg will be combined). The treatment differences will be back-transformed to present the ratios of geometric means and the corresponding 90% confidence interval (CI).

For ramucirumab SC dosing PK parameters, the t_{max} will be analyzed using a Wilcoxon rank-sum test. Estimates of the median difference based on the observed medians, 90% CIs, and p-values from the Wilcoxon test will be calculated.

Ramucirumab bioavailability will be estimated (see Section 9.4.2.1).

Comparison of AUC and C_{max} between Group 1 and Group 4 will enable to assess the effect of changing the drug product concentration on the exposure. The log-transformed C_{max} and AUC will be the response variable, and the drug product concentration (that is, Group 1 and Group 4) is the explanatory variable.

Comparison of AUC and C_{max} between Group 1 and Group 5 will enable to assess the effect of changing the volume injected at one site of injection on the exposure. The log-transformed C_{max} and AUC will be the response variable, and the volume injected (that is, Group 1 and Group 5) is the explanatory variable.

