## 4. STUDY OBJECTIVES AND ENDPOINTS

### 4.1 Primary Objectives and Endpoints

Primary Objectives	Primary Endpoints

Evaluate ramucirumab safety following a single dose in healthy participants

	

Incidence of adverse events (AEs), treatment-emergent adverse events (TEAEs), and serious adverse events (SAEs) after intravenous (IV) administration and subcutaneous (SC) administration in healthy participants

Assess injection site reactions (ISRs) following SC administration of ramucirumab using ISR questionnaire

	

Characterization and measurement of incidence and severity of ISRs (including injection site pain [ISP]) using data collected from the ISR questionnaire

Assess ramucirumab PK following a single dose of IV or SC administration

	

PK parameters:

IV: area under the concentration versus time curve (AUC) from zero to infinity (<math>AUC_{[0-\infty]}</math>), maximum observed drug concentration (<math>C_{max}</math>), time of maximum observed drug concentration (<math>t_{max}</math>)

SC: <math>AUC_{(0-\infty)}</math>, <math>C_{max}</math>, <math>t_{max}</math> after SC administration

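### For SC tmax, a primary PK parameter, the SAP sets a difference of observed medians beside a Wilcoxon-based interval, aims at similarity with no margin, and adds an undeclared log-linear model for Group 1 v 4 and 1 v 5

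*SAP*

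**What the plan says.** tmax is a primary endpoint in SAP 4.1 ("time of maximum observed drug concentration"), and protocol 9.4.2.1 says: "The primary parameters for analysis will be t_{max} , C_{max} , and AUC of ramucirumab".

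**Dose-level contrasts.** Protocol 9.4.2.2 and SAP 9.3.2 both use a Wilcoxon rank-sum test. The protocol says: "Estimates of the median difference based on the observed medians, 90% CIs, and p-values from the Wilcoxon test will be calculated". The SAP repeats this and adds a purpose, so that the "median difference based on the observed medians, 90% CIs, and p-values from the Wilcoxon test will be calculated to assess similarity or not". It names the contrast as "dose level groups 1, 4, 5 combined compared to group 2 and group 6". Neither document gives a similarity margin or names the CI method beyond this sentence.

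**Formulation contrasts.** In SAP 9.3.2, log-transformed AUC, Cmax and tmax "will be the response variable, and the drug product concentration (that is, Group 1 and Group 4) is the explanatory variable". The parallel sentence for volume reads "will be the response variable, and the volume injected (that is, Group 1 and Group 5) is the explanatory variable". The example code that follows is a linear model on the logged PK parameter. Protocol 9.4.2.2 has the same two sentences, but with Cmax and AUC only.

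**Status of inference and changes.** Protocol 9.1 says: "Formal statistical hypothesis testing is not planned". The sample-size sections of both documents say the study is not powered for hypothesis testing. Protocol 9.4 requires changes to the analysis methods to be described and justified in the SAP and the study report. SAP section 11 reports none.

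**The concern.** There are three separate problems, all on one primary PK parameter.

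1. **Estimate and interval.** Inverting the rank-sum test gives an interval for the Hodges-Lehmann shift, which is the median of all pairwise differences. The SAP places beside it a different estimator, the difference of the two sample medians. With 7 participants in one arm and peaks restricted to sampling times, the two can part noticeably.

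2. **Similarity without a margin.** With no margin, neither the estimate nor the interval has a rule for concluding similarity. A reader could then fall back on a non-significant p-value, which in groups this small is weak evidence.

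3. **Undeclared change of method.** For Group 1 v 4 and 1 v 5, tmax moves to a log-linear model with no reason given. The same parameter would be reported as a difference in hours for dose and as a geometric mean ratio for formulation, although the SAP states that nothing changed from the protocol.

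**Working it through.** **1. Plan figures.** 6 groups × 10 = 60 enrolled and 6 × 8 = 48 evaluable; both reproduce. No power, margin or effect size is stated for tmax. With 7 active participants per group, Groups 1, 4 and 5 combined against Group 2 is 3 × 7 = 21 v 7.

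**2. The two estimators on one constructed data set.** The times lie on the SC sampling grid of protocol 1.3.1 (daily to 168 h, then 264 h).

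- Pooled 350 mg, n = 21: 96 h (2 participants), 120 (2), 144 (7), 168 (7), 264 (3). The 11th value, the median, is 144 h.
- Comparison group, n = 7: 144 h (3), 264 (4). The median is 264 h.
- Difference of observed medians: 264 − 144 = 120 h.
- Pairwise differences, 21 × 7 = 147:

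| Difference (h) | −120 | −24 | 0 | 24 | 48 | 96 | 120 | 144 | 168 |
|---|---|---|---|---|---|---|---|---|---|
| Count | 9 | 21 | 33 | 6 | 6 | 28 | 28 | 8 | 8 |
| Cumulative | 9 | 30 | 63 | 69 | 75 | 103 | 131 | 139 | 147 |

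- The Hodges-Lehmann shift is the 74th value, 48 h.
- The rank-sum interval runs from the 42nd smallest to the 42nd largest value (the 106th): 0 to 120 h, at an exact level of 91% without ties. The Wilcoxon p is 0.14.

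The reported estimate would be 120 h, at the very edge of an interval whose own estimate is 48 h. The data were chosen to show the mechanism, so they say nothing about how often this happens.

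**3. Typical size by simulation.** The absorption rate of 0.3/day is from protocol 4.3. A half-life of 12 days lies within the 10 days to 2 weeks of protocol 2.1. Assumed, because the documents do not give them: one compartment, log-SD 0.35 on absorption and 0.25 on half-life, and 10% assay error.

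With tmax = ln(ka/ke)/(ka − ke) and ke = 0.693/12 = 0.0578/day:

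- ka = 0.3: ln(5.19)/0.242 = 6.80 days = 163 h
- ka = 0.2: ln(3.46)/0.142 = 8.73 days = 210 h

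SAP 9.3.1 uses actual sampling times for individual parameters, so times were spread within the collection windows. Results at 21 v 7:

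| Actual times | No true difference | Absorption 0.2/day |
|---|---|---|
| Mean gap between the two estimates | about 8 h | about 15 h |
| Gap of 24 h or more | about 3% | about 17% to 20% |
| Observed-median difference outside the rank-sum CI | 0% | 0% |

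At nominal times the 24 h figures would be about 37% and 53%. Daily spacing makes most disagreements count as at least 24 h, so those figures do not describe the planned analysis.

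**4. What a non-significant result would mean.** With absorption slowed to 0.2/day (typical tmax 163 to 210 h), p<0.10 occurs in about 40% of trials. About 60% would therefore show no significant difference. A separate model (lognormal tmax, median 150 h and CV 30% to 50%, all assumed; nominal times; 18 to 21 v 6 to 7) gives p≥0.10 in 53% to 77% of trials when the true tmax ratio is 1.25.

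**5. The log-linear switch.** Under the same lognormal assumptions, with 6 to 7 per group, a t-test on log tmax and the rank-sum test disagree at the 10% level in 3% to 8% of trials. Moving one of 7 peaks from 120 to 264 h multiplies the geometric mean by (264/120)^(1/7) = 1.119, or 12%.

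**The case against.** Four stronger readings are tempting, and the case against each is good.

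- **That the SAP judges similarity by a p-value alone.** It lists the estimate, the interval and the p-value together and sets no p-value threshold. What stands is that no margin gives the estimate or the interval a rule, so the p-value route is left open.
- **That the estimate and interval are flatly incompatible.** The CI method is not named outright, and the Wilcoxon phrase may govern only the p-values. Under a pure location shift both estimators target the same quantity, and in simulation the observed-median difference never left the rank-sum interval. What stands is that one reading pairs an interval with another estimator, and the other reading leaves the interval undefined for a primary PK parameter.
- **That the p-values contradict protocol 9.1.** That section rules out formal testing and concludes that multiplicity adjustment does not apply. Descriptive p-values, which protocol 9.4.2.2 itself plans, are compatible with it. Low power is likewise no fault in a study that claims none; it matters only if non-significance is read as similarity.
- **That the log-linear model would change the findings.** The two tests rarely disagree, and 12% of 120 h is about 14 h, less than one sampling interval. The objection does not remove the undeclared difference: tmax is in the SAP sentences, absent from the protocol's, and section 11 denies any change.

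**Conclusion.** The point holds as a moderate one and should be fixed. The undeclared addition of log tmax follows from the text alone. So do the missing margin and the fact that the sentence either mismatches estimator and interval or leaves the CI method open. The numerical effect is limited, at the mean gaps and 24 h frequencies shown for actual sampling times. These sizes, and the roughly 40% detection rate, rest on an assumed one-compartment model with assumed between-participant spread and assay error; only the absorption rate and the half-life range come from the protocol. The documents do not support saying that tmax results would be wrong or that conclusions would generally reverse.

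**What to change.** In SAP 9.3.2:

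- Report the Hodges-Lehmann shift with its matching 90% CI for every SC tmax contrast: pooled Groups 1, 4 and 5 v Group 2 and v Group 6, Group 1 v 4, and Group 1 v 5.
- Keep observed medians and ranges as description.
- Remove tmax from the log-linear model, leaving AUC and Cmax as in the protocol.
- Replace the similarity wording with interpretation of the interval. If p-values are kept, label them descriptive.

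In SAP section 11, record the departure from protocol 9.4.2.2 and the reason. Protocol 9.4 requires an amendment only for a change to a principal feature, and other changes go in the SAP and the study report, so the SAP entry should be enough.

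The cost is a small wording and programming change using a standard software option. No extra data or participants are needed.
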